20.1. Example SAS Code

1. The Example SAS code for Time to Event and Hazard Ratio

```
proc lifetest data=analysis_data;
  time aval*cnsr(1);
  strata trtp;
run;

proc phreg data=analysis_data;
  class trtp stratum;
  model aval*cnsr(1)=trtp stratum;
run;
```

2. The example SAS code for CMH model is listed as below:

```
proc freq data=analysis_data;
  tables stratum*trt*resp/ cmh alpha=0.1;
run;
```

3. The example SAS code for MMRM model is listed as below:

```
proc mixed data = analysis_data;
  class stratum trtp avisit subjid;
  model chg = base stratum trtp avisit trtp*avisit/ ddfm=kr;
  repeated avisit / subject=subjid(trtp) type=un;
  lsmeans trtp/ cl diff;
  lsmeans trtp*avisit/ slice=avisit cl diff;
run;
```

4. The example SAS code for ANCOVA model is listed as below:

```
proc mixed data = analysis_data;
  class stratum trtp;
  model chg = base stratum trtp;
```

This document is confidential.

lsmeans trtp/ cl diff;

run;

This document is confidential.

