4.1. Brief Description

This is a Phase 3b multicenter, randomized, double-blind, placebo-controlled, parallel-group study to evaluate the durability of response and safety of nemolizumab in adult subjects who participated in the nemolizumab PN LTE study (RD.06.SPR.202699) and achieved a clinical response (i.e., IGA score of 0 or 1 and ≥ 4 -point improvement in weekly average of PP NRS score from baseline of the lead-in study) at Week 52 of the LTE study.

[figure not shown]
Subjects who agree to enroll in this study must do so at the time of completion of the Week 52 visit in the LTE study (RD.06.SPR.202699) to prevent any lapse in study treatment. After the Week 52 visit of the LTE study is complete, approximately 100 subjects who choose to enter this study will be randomized 1:1 to receive either 1 or 2 injections of nemolizumab or placebo, stratified by dosing regimen. Subjects will continue to receive the same dosing regimen received in the LTE study (i.e., 1 or 2 SC injections of study drug administered every 4 weeks [Q4W]). Subjects with a body weight <90 kg in LTE study will receive a 30-mg dose. Subjects weighing ≥ 90 kg in the LTE study will receive a 60-mg dose.

Subjects' participation in the study will be up to approximately 32 weeks. The study consists of a 24-week treatment period and an 8-week follow-up period (12 weeks after their last study drug injection at Week 20).

Relapse is defined as an increase in (weekly average of the) PP NRS score ≥ 4 points from baseline or an increase in IGA score ≥ 2 from baseline at any point during the study. If a subject meets the criteria for relapse, then the subject may be considered for re-entry into the LTE study (RD.06.SPR.202699). Refer to [Figure 4-1](#) for subject transition between studies 202699 and 203890.

This document is confidential.

Figure 4-1: Subject Transition between Studies 202699 and 203890

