4.3. Determination of Sample Size

No formal sample size calculations were performed for this study. The sample size will be based on the sample size and the actual response rate of the LTE study. Based on the current assumption, it is expected that approximately 40 subjects will be randomized.

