4.4. Treatment Assignment and Blinding

Upon confirmation of eligibility for a given subject to participate in the study, a unique randomization number will be assigned to that subject via Interactive Response Technology (IRT).

This document is confidential.

The randomization number for a given subject will be used to identify the treatment arm the subject will be assigned to.

Subjects will be randomized in a 1:1 ratio to receive treatment of either Nemolizumab (CD14152) or placebo. The randomization scheme will be stratified by dosing regimen (1 or 2 injections) using the IRT system.

All attempts will be made to keep the study center staff and subjects blinded throughout the study. Members of the study center staff, including those responsible for dual-chamber syringe (DCS) preparation, will not have access to the randomized treatment assignment.

To ensure double-blind administration of study drug, the study center pharmacist(s) or other qualified personnel will prepare all Nemolizumab (CD14152) or placebo treatments, according to the current version of the pharmacy manual and assigned DCS provided by the IRT system.

As there may be detectable differences between active and placebo during the reconstitution process, the DCS is delivered for injection after the reconstitution is complete. The pharmacist (or other qualified personnel) preparing study drug should not be involved with any study assessments and should not discuss any aspects of study drug reconstitution with the subject or study staff involved in subject interviews or study assessments.

To maintain the integrity of the study blinding, the bioanalytical laboratory staff who process/analyze the anti-drug antibody (ADA) samples will not provide any information to the Sponsor, CRO, or investigational study center personnel directly involved with the ongoing conduct of the study that may lead to unblinding during the ongoing study. ADA results will be released by the bioanalytical laboratory after data base lock (DBL).

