8.1. General Methods

- All data will be listed, and summary tables will be provided.
- Unless otherwise specified, summaries will be presented for each treatment, if indicated, by visit.
- Continuous variables will be summarized using the number of observations (n), mean, standard deviation (SD), median, minimum and maximum. Categorical variables will be summarized using number of observations (n), frequency and percentages of subjects
- Unless otherwise stated, all statistical tests will be two-sided and conducted at the 5% level; all presented confidence intervals (CIs) will be two-sided 95% CIs.

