10.1. Primary Efficacy Endpoints

10.1.1. Primary Analysis of Primary Efficacy Endpoint

The primary endpoint is the time to relapse which is defined as meeting at least 1 of the following criteria:

- Increase in (weekly average of the) PP NRS score ≥ 4 points from baseline
- Increase in IGA score ≥ 2 points from baseline;

For primary endpoint, any subjects with missing data for PP NRS and IGA Score both at visit will be censored at the respective timepoint. If any one of PP NRS or IGA Score data is available for the visit, calculation for primary endpoint will be made using available results. If a subject has taken prohibited medication at any point of time during treatment period, then subject will be censored at the respective visit.

The primary endpoint will be analyzed using Cox proportional hazard model with treatment group, dosing regimen as a factor, and baseline PP NRS score and IGA score as covariates on ITT population. The estimated hazard ratio and the corresponding 95% CI will be presented. A supportive analysis also will be performed using Per-Protocol Population.

Kaplan-Meier survival plots will also be presented for time to relapse. The median time, 25th and 75th quantiles along with corresponding CI will be presented using ITT/PP.

Censoring rule for primary endpoint variable is as follows:

Situation	Date of Progression or Censoring	Outcome
Relapse as described	Date of Relapse	Event
Subject withdrawn without relapse	Date of last efficacy assessment (PP NRS and IGA) prior to withdrawal	Censored
Treatment Discontinuation	Date of last efficacy assessment (PP NRS and IGA) prior to Treatment Discontinuation	Censored
Prohibited medication without relapse	Date of last efficacy assessment (PP NRS and IGA) prior to prohibited medication	Censored
Completes the study without relapse	Date of Week 24 completion	Censored
No Efficacy assessment	Date of study Day 1	Censored

This document is confidential.

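### The primary hazard ratio has no pre-specified method if an arm has no relapse, and its ties and interval methods are left to software defaults

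*SAP*

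**What the plan says.** SAP 10.1.1 fits a Cox model with treatment, dosing regimen and "baseline PP NRS score and IGA score as covariates on ITT population". On output it says "The estimated hazard ratio and the corresponding 95% CI will be presented", and it adds Kaplan-Meier plots with the median and quartiles. It names no ties method, no type of interval and no rule for an arm without events.

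The only matching code is in SAP 20.1, under the label "The Example SAS code for Time to Event and Hazard Ratio". Its PHREG model statement is "model aval*cnsr(1)=trtp stratum", with nothing after a slash. It also leaves out the two baseline covariates that 10.1.1 requires.

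The only fallback for the primary model is in the protocol (synopsis and 14.3.1). It covers non-proportional hazards and nothing else. By contrast, SAP 10.2 does pre-specify what to do if the secondary MMRM fails to converge.

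On size, SAP 4.3 says "it is expected that approximately 40 subjects will be randomized" and SAP 4.1 says "approximately 100 subjects who choose to enter this study will be randomized 1:1". Protocol 14.1 agrees with 40. No power, event count or relapse rate is given anywhere.

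**The concern.** Everyone randomized is a Week 52 responder, and one arm carries on with the same drug. With about 20 subjects in that arm, no relapse at all is a realistic result. Ordinary partial likelihood then has no finite maximum for the treatment coefficient, so the primary estimand's summary measure and its Wald interval cannot be reported. The team would have to choose a substitute after unblinding, in the very case where the treatment effect looks strongest.

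A smaller matter is ties. IGA is read every 4 weeks and PP NRS is averaged weekly, so relapse times may coincide. Breslow's approximation pulls the hazard ratio towards 1 when ties are heavy.

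**Working it through.** The plan has no calculation of its own to reproduce. That PHREG defaults to Breslow ties and Wald limits is a property of the software, not something the documents state.

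**Inputs.** From the SAP: about 40 subjects (4.3) or 100 (4.1), allocated 1:1 (4.4), hence 20 or 50 per arm; two-sided 5% level (8.1). Assumed: relapse risks, over a range.

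**Why no events means no estimate.** If all events are on placebo, the Breslow log partial likelihood is −Σ dⱼ log(n₀ⱼ + n₁ⱼ e^β), where dⱼ is the number of events at time j, and n₀ⱼ and n₁ⱼ are the numbers at risk on placebo and nemolizumab. It rises steadily as β falls, so the hazard ratio goes to 0. Adding covariates does not cure this.

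**Chance of no nemolizumab relapse**, (1 − p)ⁿ:

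| True risk p | n = 20 | n = 50 |
|---|---|---|
| 5% | 0.95²⁰ = 36% | 0.95⁵⁰ = 7.7% |
| 10% | 0.90²⁰ = 12% | 0.90⁵⁰ = 0.5% |
| 15% | 0.85²⁰ = 3.9% | – |
| 20% | 0.80²⁰ = 1.2% | – |

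**Worked case: 0/20 against 10/20**, with placebo events 1, 2, 2, 2, 2, 1 over the six visits (treatment-only model). The ordinary fit diverges; the optimiser stopped at its search limit, with a hazard ratio near 0.000006. Firth with Efron ties gives 0.036, with 95% profile-likelihood limits 0.0003 to 0.28. The log-rank test gives chi-square 13.2, p = 0.0003.

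**Size of the ties effect.** Simulation with 20 per arm, exponential relapse over 24 weeks, a treatment-only model and 1,000 runs per row. Entries are the Breslow/Efron ratio of hazard ratios in estimable runs.

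| Placebo relapse | Assumed HR | Nominal 4-week times | Visit days within windows | Weekly times | SD of log HR |
|---|---|---|---|---|---|
| 40% | 0.20 | 1.03 | 1.005 | 1.007 | 0.67 |
| 60% | 0.20 | 1.06 | 1.010 | 1.014 | 0.64 |
| 60% | 0.35 | 1.05 | 1.008 | 1.011 | 0.54 |
| 80% | 0.20 | 1.10 | 1.018 | 1.026 | 0.54 |
| 80% | 0.35 | 1.08 | 1.015 | 1.021 | 0.43 |

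With 90% relapse on placebo and 10% on nemolizumab (true HR ln 0.9/ln 0.1 = 0.046), the nominal-visit shift reaches 16-18%.

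Against sampling error: exp(1.96 × 0.43) = 2.3 and exp(1.96 × 0.67) = 3.7, so the 95% limits lie about 2.3 to 3.7 times either side of the estimate. In the 80%/0.20 row the shift is ln 1.103/0.54 = 0.18 of a standard deviation.

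**The case against.** The code is headed as an example, and the zero-event risk depends on rates nobody has stated: about 1% at 20% relapse, and smaller again if the size is 100. Both points are fair. But the SAP text is as silent as the code, so nothing overrides the defaults, and the protocol and SAP 4.3 both plan for 40.

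A second objection is that the trial would still be interpretable. Kaplan-Meier estimates describe durability in the placebo arm, and the LIFETEST step in 20.1 would print a log-rank test that works with no events in one arm. That stands, and a reader who took the hazard ratio to be the only stated primary result would be wrong. It does not close the gap: 10.1.1 does not name the log-rank test, and that test supplies neither the hazard ratio nor its interval.

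Three stronger readings are tempting but not supported.

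- *The hazard ratio will be attenuated by Breslow ties.* The larger shifts need every event on a nominal 4-week visit. The SAP gives no rule for deriving the relapse date. Visits have windows of ±1 to ±5 days, early-termination and unscheduled IGA readings occur, PP NRS is averaged weekly, and relapse counts at any time. The by-visit wording in 10.1.1 allows nominal times but does not require them.
- *The Wald interval covers badly.* Coverage of 59%, 84% and 92% at 5%, 10% and 15% relapse arises only if fits with no estimate count as misses. Dividing by the estimable share (64%, 88%, 96%) gives about 92%, 96% and 96%, and direct simulation among estimable fits gave 91-97%. The loss is almost entirely non-estimability.
- *Firth should be the primary estimator in every dataset.* That is debatable. Among estimable trials it moved the hazard ratio towards 1, relative to plain Efron, by 31-36%, 23-25% and 16-18% at 5%, 10% and 15% relapse. That compares it with the ordinary fit, not with the truth; at 10-20% relapse it showed little bias.

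**Conclusion.** The gap is real, and its main part is the missing zero-event rule. If relapse on continued nemolizumab is about 10% or less and the size is about 40, the planned hazard ratio has roughly a 12-36% chance of not existing over the 5-10% range. At 20% relapse or more the risk is about 1% or less. At 100 subjects it matters only near 5%. These figures assume independent subjects with a common risk and full follow-up. They are minimums for the planned model, because three further terms with few events can only add to sparse-data trouble.

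The ties default is secondary: about 0.5-3% on the time scales the documents most readily suggest, about 3-10% (more in extreme cases) on nominal visits, and not enough to change a conclusion. Efron is still the better setting and costs nothing.

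**What to change.** In SAP 10.1.1, state that the primary Cox model uses Efron ties and profile-likelihood limits. State also that if either arm has no relapse, or the ordinary fit does not converge, the reported hazard ratio comes from Firth's penalised likelihood with profile-likelihood limits. The event count should be a trigger in its own right, since an optimiser can stop at an arbitrarily small hazard ratio.

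In SAP 20.1, add `ties=efron risklimits=pl` to the model statement, show the `firth` variant for the triggered case, and put back the baseline PP NRS and IGA covariates. A rule for the relapse date would settle how heavy the ties are, and 4.1 and 4.3 should give one sample size.

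The cost is a sentence or two and a few code options, with no change to design or data collection. The downside is that Firth gives a less extreme hazard ratio than the ordinary fit in sparse data. Limiting it to the triggered cases contains that. In treatment-only simulations its profile limits covered 93-97%; this has not been checked for the full covariate model.

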20.2. Potentially Clinically Significant Ranges

Potentially clinically significant ranges for Hematology parameters are defined in [Table 20-1](#).

Table 20-1 Potentially Clinically Significant Ranges for Hematology Parameters

Test Parameter	Test Parameter Code	Normal Range Lower Limit (LLN)	Normal Range Upper Limit (ULN)	Potentially Clinically Significant Ranges
Basophils ($\times 10^9/L$)	BASO	0.00	0.20	> 0.2 at post-baseline, if baseline value ≤ 0.2
Eosinophils ($\times 10^9/L$)	EOS	0.00	0.57	> 0.7 at post-baseline, if baseline value ≤ 0.7
Hematocrit (L/L)	HCT	0.39 (12-<59 years old, Male)	0.54 (12-<59 years old, Male)	< 0.30 at post-baseline, if baseline value ≥ 0.30
		0.37 (≥ 59 years old, Male)	0.51 (≥ 59 years old, Male)	> 0.6 at post-baseline, if baseline value ≤ 0.6
		0.34 (Female)	158.00 (Female)	
Hemoglobin (g/L)	HGB	127 (12-<59 years old, Male)	181 (12-<59 years old, Male)	Male < 100 at post-baseline, if baseline value ≥ 100
		116 (12-<59 years old, Female)	164 (12-<59 years old, Female)	Male ≥ 200 at post-baseline, if baseline value < 200
		125 (≥ 59 years old, Male)	170 (≥ 59 years old, Male)	Female < 90 g/L at post-baseline and ≥ 90 g/L at baseline
		115 (≥ 59 years old, Female)	158 (≥ 59 years old, Female)	Female ≥ 180 g/L at post-baseline and < 180 g/L at baseline
Leukocytes ($\times 10^9/L$)	WBC	3.80	10.70	< 3.0 at post-baseline, if baseline value ≥ 3.0
				> 15.0 at post-baseline, if baseline value ≤ 15.0
Lymphocytes ($\times 10^9/L$)	LYM	0.91 (18 – <59 years old)	4.28 (18 – <59 years old)	< 0.8 at post-baseline, if baseline value ≥ 0.8
		0.80 (≥ 59 years old)	3 (≥ 59 years old)	> 4.28 at post-baseline, if baseline value ≤ 4.28 (age 18 – < 59); > 3.00 at post-baseline, if baseline value ≤ 3.00 (age ≥ 59)
Monocytes ($\times 10^9/L$)	MONO	0.12	0.92	> 0.92 at post-baseline, if baseline value ≤ 0.92

This document is confidential.

Statistical Analysis Plan for Interventional Studies

Sponsor: Galderma S.A./Galderma R&D, LLC; Protocol No.: RD.06.SPR.203890

Neutrophils, Segmented (GI/L)	NEUTSG	1.96	7.23	< 1.5 at post-baseline, if baseline value is ≥ 1.5
				> 9 at post-baseline, if baseline value is ≤ 9
Platelets (x10 ⁹ /L)	PLAT	140 (18 - <60 years old)	400 (18 - <60 years old)	< 100 at post-baseline, if baseline value ≥ 100
		130 (≥ 60 years old)	394 (≥ 60 years old)	> 700 at post-baseline, if baseline value ≤ 700

This document is confidential.

Potentially clinically significant ranges for Blood Chemistry parameters are defined in [Table 20-2](#) Potentially Clinically Significant Ranges for Blood Chemistry Parameters.

Table 20-2 Potentially Clinically Significant Ranges for Blood Chemistry Parameters

Test Parameter	Test Parameter Code	Normal Range Lower Limit (LLN)	Normal Range Upper Limit (ULN)	Potentially Clinically Significant Ranges
Aspartate Aminotransferase (U/L)	AST	8.00	40.00	> 3 x ULN at post-baseline, if baseline value \leq 3 x ULN
Alkaline Phosphatase (U/L)	ALP	55 (< 19 years old, Male) 45 (< 19 years old, Female) 40 (\geq 19 years old, Male) 35 (\geq 19 years old, Female)	149 (< 19 years old, Male) 87 (< 19 years old, Female) 129 (\geq 19 years old, Male) 104 (\geq 19 years old, Female)	> 2.5 x ULN at post-baseline, if baseline value \leq 2.5 x ULN
Alanine Aminotransferase (U/L)	ALT	5 (Male) 4 (Female)	48 (Male) 43 (Female)	> 3 x ULN at post-baseline, if baseline value \leq 3 x ULN
Bilirubin (umol/L)	BILI	3.00	21.00	> 1.5 x ULN at post-baseline, if baseline value \leq 1.5 * ULN
Calcium (mmol/L)	CA	2.07	2.64	< 2 at post-baseline, if baseline value \geq 2
Chloride (mmol/L)	CL	94.00	112.00	> 2.9 at post-baseline, if baseline value \leq 2.9 < 94 at post-baseline, if baseline value \geq 94 > 115 at post-baseline, if baseline value \leq 115
Cholesterol (mmol/L)	CHOL	2.95 (< 20 years old, Male)	5.12 (< 20 years old, Male)	> 7.75 at post-baseline, if baseline value \leq 7.75 (Female \leq 60 years old, Male \leq 70 years old); > 8.28 at post-baseline, if baseline value \leq 8.28 (Female $<$ 60 - 70 years old); > 7.76 at post-baseline, if baseline value \leq 7.76 (Male $>$ 70 years old); > 9.10 at post-baseline, if baseline value \leq 9.10 (Female $>$ 70 years old)
		3.23 (< 20 years old, Female)	5.48 (< 20 years old, Female)	

This document is confidential.

Test Parameter	Test Parameter Code	Normal Range Lower Limit (LLN)	Normal Range Upper Limit (ULN)	Potentially Clinically Significant Ranges
		3.31 (20 - < 30 years old, Male)	6.10 (20 - < 30 years old, Male)	
		3.31 (20 - < 30 years old, Female)	5.64 (20 - < 30 years old, Female)	
		3.88 (30 - < 40 years old, Male)	6.83 (30 - < 40 years old, Male)	
		3.65 (30 - < 40 years old, Female)	6.21 (30 - < 40 years old, Female)	
		4.19 (40 - < 50 years old, Male)	7.24 (40 - < 50 years old, Male)	
		4.01 (40 - < 50 years old, Female)	6.85 (40 - < 50 years old, Female)	
		4.40 (50 - < 60 years old, Male)	7.53 (50 - < 60 years old, Male)	
		4.42 (50 - < 60 years old, Female)	7.53 (50 - < 60 years old, Female)	
		4.53 (60 - < 70 years old, Male)	7.71 (60 - < 70 years old, Male)	
		4.86 (60 - < 70 years old, Female)	8.28 (60 - < 70 years old, Female)	
		4.58 (\geq 70 years old, Male)	7.76 (\geq 70 years old, Male)	
		5.35 (\geq 70 years old, Female)	9.10 (\geq 70 years old, Female)	
Creatinine (umol/L)	CREAT	40 (18 - < 50 years old, Male)	110 (18 - < 50 years old, Male)	> 1.5 x ULN at post-baseline, if baseline value \leq 1.5 x ULN
		31 (18 - < 50 years old, Female)	101 (18 - < 50 years old, Female)	
		40 (50 - < 70 years old, Male)	119 (50 - < 70 years old, Male)	
		31 (50 - < 70 years old, Female)	101 (50 - < 70 years old, Female)	
		40 (70 - < 80 years old, Male)	137 (70 - < 80 years old, Male)	

This document is confidential.

Statistical Analysis Plan for Interventional Studies

Sponsor: Galderma S.A./Galderma R&D, LLC; Protocol No.: RD.06.SPR.203890

Test Parameter	Test Parameter Code	Normal Range Lower Limit (LLN)	Normal Range Upper Limit (ULN)	Potentially Clinically Significant Ranges
		31 (70 - < 80 years old, Female)	110 (70 - < 80 years old, Female)	
		40 (\geq 80 years old, Male)	145 (\geq 80 years old, Male)	
		31 (\geq 80 years old, Female)	128 (\geq 80 years old, Female)	
Creatine Kinase (U/L)	CK	39 (Male)	308 (Male)	> 2.5 x ULN at post-baseline, if baseline value \leq 2.5 x ULN
		26 (Female)	192 (Female)	
Direct Bilirubin (umol/L)	BILDIR	<2.00	7.00	> 1.5 x ULN at post-baseline, if baseline value \leq 1.5 x ULN
Gamma Glutamyl Transferase (U/L)	GGT	10 (< 59 years old, Male)	61 (< 59 years old, Male)	> 2.5 x ULN at post-baseline, if baseline value \leq 2.5 x ULN
		4 (< 59 years old, Female)	49 (< 59 years old, Female)	
		10 (\geq 59 years old, Male)	50 (\geq 59 years old, Male)	
		5 (\geq 59 years old, Female)	50 (\geq 59 years old, Female)	
Glucose (mmol/L)	GLUC	3.90	5.60	< 3 at post-baseline, if baseline value \geq 3 > 13.9 at post-baseline, if baseline value \leq 13.9
Potassium (mmol/L)	K	3.5	5.2	< 3.5 at post-baseline, if baseline value \geq 3.5 > 5.5 at post-baseline, if baseline value \leq 5.5
Sodium (mmol/L)	SODIUM	132 (18 – < 59 years old)	147 (18 – < 59 years old)	< 129 at post-baseline, if baseline value \geq 129
		135 (\geq 59 years old)	145 (\geq 59 years old)	> 150 at post-baseline, if baseline value \leq 150
Triglycerides (mmol/L)	TRIG	0.42 (< 20 years old, Male)	1.67 (< 20 years old, Male)	> 3.69 at post-baseline, if baseline value \leq 3.69
		0.44 (< 20 years old, Female)	1.40 (< 20 years old, Female)	
		0.50 (20 – < 30 years old, Male)	2.81 (20 – < 30 years old, Male)	
		0.41 (20 – < 30 years old, Female)	1.63 (20 – < 30 years old, Female)	

This document is confidential.

Test Parameter	Test Parameter Code	Normal Range Lower Limit (LLN)	Normal Range Upper Limit (ULN)	Potentially Clinically Significant Ranges
		0.56 (30 – < 40 years old, Male)	3.62 (30 – < 40 years old, Male)	
		0.44 (30 – < 40 years old, Female)	1.99 (30 – < 40 years old, Female)	
		0.62 (40 – < 50 years old, Male)	3.69 (40 – < 50 years old, Male)	
		0.51 (40 – < 50 years old, Female)	2.42 (40 – < 50 years old, Female)	
		0.65 (50 – < 60 years old, Male)	3.61 (50 – < 60 years old, Male)	
		0.59 (50 – < 60 years old, Female)	2.96 (50 – < 60 years old, Female)	
		0.65 (≥ 60 years old, Male)	2.94 (≥ 60 years old, Male)	
		0.63 (≥ 60 years old, Female)	2.71 (≥ 60 years old, Female)	
Urate (mmol/L)	URATE	125 (< 50 years old, Male)	488 (< 50 years old, Male)	> 494 at post-baseline, if baseline value ≤ 494 (Male); > 446 at post-baseline, if baseline value ≤ 446 (Female)
		125 (< 50 years old, Female)	428 (< 50 years old, Female)	
		149 (50 - < 70 years old, Male)	494 (50 - < 70 years old, Male)	
		149 (50 - < 70 years old, Female)	446 (50 - < 70 years old, Female)	
		149 (≥ 70 years old, Male)	494 (≥ 70 years old, Male)	
		149 (≥ 70 years old, Female)	446 (≥ 70 years old, Female)	
Urea Nitrogen (mmol/L)	UREAN	1.40 (< 70 years old)	8.60 (< 70 years old)	> 8.6 at post-baseline, if baseline value ≤ 8.6 (<70 years old); > 10.4 at post-baseline, if baseline value ≤ 10.4 (70 - <80 years old); > 12.1 at post-baseline, if baseline value ≤ 12.1 (≥ 80 years old)

This document is confidential.

Statistical Analysis Plan for Interventional Studies

Sponsor: Galderma S.A./Galderma R&D, LLC; Protocol No.: RD.06.SPR.203890

Test Parameter	Test Parameter Code	Normal Range Lower Limit (LLN)	Normal Range Upper Limit (ULN)	Potentially Clinically Significant Ranges
		1.40 (70 - < 80 years old)	10.40 (70 - < 80 years old)	
		1.40 (\geq 80 years old)	12.10 (\geq 80 years old)	

This document is confidential.

Potentially clinically significant ranges for vital signs parameters are defined in [Table 20-3](#).

Table 20-3 Potentially Clinically Significant Ranges for Vital Signs Parameters

Test Parameter	Test Parameter Code	Potentially Clinically Significant Ranges
Pulse rate (beats/min)	PULSE	≥120 bpm and increase from baseline ≥20 bpm
		≤50 bpm and decrease from baseline ≥20 bpm
Diastolic blood pressure (mmHg)	DIABP	≥110 mmHg and increase from baseline ≥10 mmHg
		≤45 mmHg and decrease from baseline ≥10 mmHg
Systolic blood pressure (mmHg)	SYSBP	≥160 mmHg and increase from baseline ≥20 mmHg
		≤95 mmHg and decrease from baseline ≥20 mmHg
Weight	WEIGHT	≥5% increase from baseline
		≥5% decrease from baseline

This document is confidential.

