Summary of the number and percentage of subjects who met criteria of potential clinically significant (CS) value will be summarized (scheduled visits only) for hematology, chemistry. Last, worst and maximum post-baseline results will also be included in the summaries. Potentially CS ranges are listed in [Section 20.2](#).

For statistical and graphical summaries of the laboratory tests, values below or above the limit of detection (e.g. '< 3' or '> 500') are substituted with the lower limit of detection minus 1% for values below the lower limit and are substituted with the upper limit of detection plus 1% for values above the upper limit (e.g. '< 3' is substituted by '2.97', '> 500' is substituted by '505'). In data listings, the values are shown including the < or > sign.

Distribution of continuous hematology and chemistry laboratory data (in particular, Aspartate Aminotransferase (AST), Alanine Aminotransferase (ALT), Alkaline Phosphatase (ALP), Total Bilirubin (BILI), Creatinine Kinase (CK) and Leukocytes (WBC)) will be displayed graphically as boxplot by treatment group for baseline and for each scheduled visits and the maximum post-Baseline (including unscheduled visits in the derivation) values.

By-subject listing will be presented for all laboratory data. By-subject listing for subjects with at least one abnormal result (out of reference range) will be provided for hematology and clinical chemistry. By-subject listing for subjects with at least one potentially CS result will be provided for hematology, clinical chemistry.

All laboratory data will be listed for the Safety population.

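### SAP Table 20-2 labels urate in mmol/L, but its limits and fixed cut-offs fit umol/L; in the labelled unit the urate flag can never fire

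*SAP*

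**What the plan says.** SAP Section 20.2, Table 20-2, gives the urate unit as mmol/L. The lower normal limits begin at "125 (< 50 years old, Male" and are 149 from age 50. The upper limits run from 428 to 494, for example "494 (50 - < 70 years old, Male". The PCS criterion is "> 494 at post-baseline, if baseline value ≤ 494 (Male); > 446 at post-baseline, if baseline value ≤ 446 (Female".

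SAP Section 13.2.1 puts these criteria to use: "Summary of the number and percentage of subjects who met criteria of potential clinically significant (CS) value will be summarized" for hematology and chemistry. It names Section 20.2 as the source of the ranges and adds a by-subject listing of anyone with at least one PCS result. The planned chemistry outputs are Tables 14.3.4.1.2.3 and 14.3.4.1.2.5. Uric acid is among the protocol's chemistry tests (Protocol 12.5.2), and Protocol 14.4 commits to the PCS summary.

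Section 13.2.1 treats reference ranges separately. They come from the central laboratory through its manual, and the shift tables use them. A further by-subject listing covers any result outside the reference range.

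Table 20-1 gives "Hematocrit (L/L" as the hematocrit unit. The male upper limit is "0.54 (12-<59 years old, Male" and the female one is "158.00 (Female". The high PCS criterion in that row is "> 0.6 at post-baseline, if baseline value ≤ 0.6", with no split by sex.

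**The concern.** A threshold printed in the wrong unit is harmless until someone programs it as written. Most of the enzyme, bilirubin and creatinine criteria in Table 20-2 are multiples of the upper limit of normal, so they scale with whatever unit the laboratory reports. Urate does not: its cut-offs are plain numbers. If the analysis dataset is standardised to the labelled unit, the rule cannot be met, and a zero produced by the unit looks exactly like a true zero. Safety is the trial's only secondary objective, and this output is meant to pick out marked laboratory changes.

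The hematocrit limit deserves attention for a simpler reason: a volume fraction cannot exceed 1, so 158.00 L/L cannot be right.

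**Working it through.** **Inputs.** Urate unit mmol/L, lower limits 125 to 149, upper limits 428 to 494, cut-offs 494 (male) and 446 (female); sodium upper limit 147 mmol/L at ages 18 to under 59 (all Table 20-2). Hematocrit unit L/L, female upper limit 158.00, fixed high cut-off 0.6; hemoglobin upper limit 158 g/L for women aged 59 or over (all Table 20-1). The plan states no derived figure to reproduce. The check is of units and of the written rule.

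**1. Scale in the labelled unit.** 494 / 147 = 3.36 and 446 / 147 = 3.03. As labelled, a urate result would have to exceed three times the sodium upper limit before it was flagged. Taking a urate molar mass of about 168.1 g/mol (an assumption, not in the documents), 494 mmol/L is 494 × 168.1 / 1000 ≈ 83 g/L. Label and numbers cannot both be right.

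**2. Scale in umol/L.** Dividing by 1000, the limits of 125 to 494 umol/L become 0.125 to 0.494 mmol/L. Under the same molar mass that is about 2.1 to 8.3 mg/dL. Table 20-2 already uses umol/L for creatinine, bilirubin and direct bilirubin.

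**3. The rule applied as written.** Flag if the post-baseline value exceeds the cut-off and the baseline value is at or below it. The values below are illustrative.

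| Stored unit | Baseline | Post-baseline | Male (494) | Female (446) |
|---|---|---|---|---|
| mmol/L | 0.4 | 0.6 | no flag | no flag |
| mmol/L | 0.4 | 1.2 | no flag | no flag |
| umol/L | 400 | 600 | flag | flag |

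In mmol/L the baseline condition is always true and the post-baseline condition is never true, so the count is zero by construction. In umol/L the rule works with no change to the numbers.

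**4. Hematocrit.** 158.00 is more than 1, so it is impossible in L/L. It equals the hemoglobin upper limit for older women in the next parameter of the table, which suggests a copying slip. It sits in the normal-range column, and the PCS rule does not refer to it. A woman going from 0.45 to 0.62 meets the high criterion, because 0.62 > 0.6 and 0.45 ≤ 0.6. Correcting the limit changes no PCS flag.

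**The case against.** The strongest reply is that the harm depends on a fact the documents do not settle. Apart from this label, nothing states the unit in which the central laboratory reports urate. If it is umol/L, as the figures suggest, every cut-off works and the error is one wrong prefix. That stands, and it is why the consequence is stated as conditional.

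The second reply is that other outputs would show a high urate even if the PCS flag failed: the out-of-range listing, the shift tables, the worst and maximum post-baseline summaries, and the investigator's review of each out-of-range result under Protocol 12.5. That also stands. What would be lost is the PCS summary and listing for this analyte, not all sight of it.

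Third, tables can be damaged in text conversion; a cut-off of 2.9 that fits calcium appears in the chloride row. The cells are worth checking in the source PDF. But the micro prefix came through for three other analytes in the same table, and hemoglobin still holds its own 158, so displacement does not readily explain either error.

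A reader might infer from the 158.00 that high hematocrit in women could not be flagged, or that no woman could shift to High. The documents do not support either. The PCS flag uses the fixed 0.6, and SAP 13.2.1 takes reference ranges from the central laboratory. The shift table would suffer only if Table 20-1 were loaded in place of those ranges, which the SAP does not plan.

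**Conclusion.** The point holds for urate as written. In the labelled unit, the cut-offs are 1000-fold too high and the PCS summary and listing would report zero regardless of the data. This rests on two things: the rule being applied literally, and the data being stored in mmol/L. A reader might take the zero as certain; it is not, because with data in umol/L only the label is wrong.

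The female hematocrit limit is a separate misprint. It has no effect on the PCS flag, nor on shift tables built on central laboratory ranges.

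Both are minor. They concern safety tabulation only: the primary endpoint is untouched, and no adverse event of special interest is defined by urate or hematocrit (Protocol 12.7.2; SAP 13.1). The urate item still merits correction because it is a decision threshold, and the resulting output would give no sign of the fault.

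**What to change.** Change the urate unit in Table 20-2 to umol/L. This is one cell. The alternative is to keep mmol/L and divide every urate figure by 1000: six lower limits, six upper limits and the two cut-offs (to 0.494 and 0.446). Confirm the choice against the central laboratory's reporting unit and the unit held in the analysis dataset before programming.

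Replace the female hematocrit upper limit in Table 20-1 with the central laboratory's value. The documents do not give that value, so none is proposed here. While the appendix is open, check both tables line by line against the laboratory manual. The cost is a small SAP correction, with no change to data collection or trial conduct.
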